5.5. Efficacy evaluation

All efficacy analyses will be conducted using the EP.

Image quality

Frequency of images with very poor, poor, fair, good and very good quality will be presented.

Diagnostic quality

Diagnosis assessment (Yes/No) and reason for impossible diagnosis will be tabulated. Diagnosis when available will be listed.

Listing of all efficacy data will be presented in CSR appendix 16.2.6.

5.6. Safety Evaluation

All safety analyses will be conducted using the SP.

5.6.1. Extent of Exposure

Extent of exposure will present the DOTAREM® administration: total volume injected, type of injection, number of injections (1 or 2), nature of package, and volume of vial and pre-filled syringe used. Total dose injected (mL/kg), calculated by dividing the total volume of DOTAREM® administered by the body weight will be presented as well.

Summary statistics for quantitative variable will be calculated for total volume injected and total dose injected. Frequency and percentages will be calculated for other criteria.

CONFIDENTIAL	FORM STATISTICAL ANALYSIS PLAN N° DGD-55-003 VERSION N° 2 DATED: 26 FEBRUARY 2018 (REF I011622)	F015830-01 Page 18 / 49
--------------	---	----------------------------

Listing of exposure will be presented in CSR appendix 16.2.5.

5.6.2. Primary safety endpoint: NSF

The number and percentage of patients with any suspicion of NSF will be presented.

For patients having any suspicion of NSF, the reasons of the suspicion will be tabulated

Among patient having any suspicion of NSF, the number and percentage of patients with a confirmatory biopsy or not (and the reason if not) will be presented.

Among patients having a confirmatory biopsy, the number and percentage of patients with a final diagnosis of NSF or not (and the reason if not) will be presented.

Listing of NSF suspicion and diagnosis will be presented in CSR appendix 16.2.9.1

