1.1. Study objectives

The primary objective of this study is to prospectively estimate the incidence of NSF in patients with moderate to severe renal impairment after administration of DOTAREM®. Patients will be followed during a two-year period after administration of DOTAREM®, to assess if signs or symptoms suggestive of NSF have appeared.

The secondary objectives of the study are:

- to collect a large number of data concerning the general safety profile of DOTAREM® during patient inclusion and MR examination,
- to collect information regarding MRI indication,
- to collect conditions of use/administration of the product in this specific population of patients,
- to collect efficacy data (image and diagnostic quality).

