3.5. Handling of dropouts or missing data

If the start date of an adverse event is missing, then the adverse event occurs after the DOTAREM® injection.

No replacement of missing data is planned in this study.

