5.2. Data Sets Analysed and protocol deviations

Data sets analysed

There will be three patient populations defined for this study: all-included population (AIP), safety population (SP) and efficacy population (EP).

The all-included population (AIP) will include all patients who have a questionnaire partly or fully filled in. This population will be used for the description of disposition of patients, protocol deviations and demographic data.

The safety population (SP) will include all patients receiving at least one injection of contrast media regardless of the quantity. This population will be used to evaluate the NSF occurrence, to describe administration modalities, for analysis of adverse events, laboratory data, other safety observations, medical events and concomitant medications presentation. Furthermore, demographic data and medical history will be presented using this population as well.

The efficacy population (EP) will include all patients who have an available imaging assessment.

The following table describes how the above-defined patients populations will be used in the different analyses conducted.

CONFIDENTIAL	
FORM STATISTICAL ANALYSIS PLAN N° DGD-55-003 VERSION N° 2 DATED: 26 FEBRUARY 2018 (REF I011622)
	F015830-01 Page 14 / 49
--------------	---	----------------------------

Analysed populations

Analysed Populations	AIP	SP	EP
Population characteristics	✓(only Demographics)	✓	
Exposure		✓	
Efficacy assessment			✓
Safety assessment : Main criterion		✓	
Safety assessment : Secondary criteria (AE, laboratory data and other safety observation)		✓	
Concomitant medications		✓	

Frequency and percentages of patients in each population will be presented. A listing showing the distribution of each patient in the populations will also be provided in CSR appendix 16.2.3.

Protocol deviations

A protocol deviation is any change, divergence, or departure from the study design or procedures defined in the protocol that might significantly affect the completeness, accuracy, and/or reliability of the study data or that might significantly affect a patient's rights, safety, or well-being. Protocol deviations are to be displayed in the Clinical Study Report (CSR) as a metric of the feasibility and reliability of the study.

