7.1. Clinical study report in-text tables, figures and listings

7.2. Contents of clinical study report section 14

Table 14.1.1.1 Patient Overall Disposition - All Included Population

	Total (N=XXX)
Number of Patients not Prematurely Withdrawn	xxx (xx.x%)
Number of Patients Prematurely Withdrawn	xxx (xx.x%)
Reason of Withdrawal	
Retraction of Patient Consent	xxx (xx.x%)
Adverse Event	xxx (xx.x%)
Patient Lost to Follow-up	xxx (xx.x%)
Technical Incident	xxx (xx.x%)
Death	xxx (xx.x%)
Medical Decision	xxx (xx.x%)
Other	xxx (xx.x%)

#: (n row / N included) * 100.

Source: Listing 16.2.1.2.

Table 14.1.1.2 Disposition by Visit - All Included Population

	General Questionnaire (N=XXX)	Follow-up 1 (N=XXX)	Follow-up 2 (N=XXX)	Follow-up 3 (N=XXX)	At Least One Follow- up Visit
Number of Patients	xxx (xx.x%)	xxx (xx.x%)	xxx (xx.x%)	xxx (xx.x%)	xxx (xx.x%)

#: (n row / N included) * 100.

Source: Listing 16.2.1.1.

Table 14.1.1.3 Disposition by Site - All Included Population

	Total (N=XXX)
Argentina	Site 29 xxx (xx.x%)
	Site 30 xxx (xx.x%)
	Site 31 xxx (xx.x%)
Belgium	Site 1 xxx (xx.x%)

CONFIDENTIAL	FORM STATISTICAL ANALYSIS PLAN N° DGD-55-003 VERSION N° 2 DATED: 26 FEBRUARY 2018 (REF I011622)	F015830-01 Page 25 / 49
--------------	---	----------------------------

Total (N=XXX)		
	Site 2	xxx (xx.x%)
	Site 28	xxx (xx.x%)
Brazil	Site 3	xxx (xx.x%)
Columbia	Site 32	xxx (xx.x%)
	Site 33	xxx (xx.x%)
	Site 34	xxx (xx.x%)
France	Site 6	xxx (xx.x%)
	Site 26	xxx (xx.x%)
Germany	Site 8	xxx (xx.x%)
	Site 27	xxx (xx.x%)
India	Site 10	xxx (xx.x%)
Italy	Site 12	xxx (xx.x%)
	Site 13	xxx (xx.x%)
	Site 14	xxx (xx.x%)
Korea	Site 15	xxx (xx.x%)
	Site 16	xxx (xx.x%)
	Site 17	xxx (xx.x%)
	Site 18	xxx (xx.x%)
Spain	Site 19	xxx (xx.x%)
	Site 20	xxx (xx.x%)
	Site 35	xxx (xx.x%)
Turkey	Site 23	xxx (xx.x%)
	Site 37	xxx (xx.x%)
United Kingdom	Site 24	xxx (xx.x%)
	Site 25	xxx (xx.x%)
Uruguay	Site 36	xxx (xx.x%)
United States of America	Site 38	xxx (xx.x%)
	Site 39	xxx (xx.x%)

CONFIDENTIAL	FORM STATISTICAL ANALYSIS PLAN N° DGD-55-003 VERSION N° 2 DATED: 26 FEBRUARY 2018 (REF I011622)	F015830-01 Page 26 / 49
--------------	---	----------------------------

Total (N=XXX)	
Site 40	xxx (xx.x%)
Site 41	xxx (xx.x%)

#: (n row / N included) * 100.

Source: Listing 16.2.1.1.

Table 14.1.1.4 Centre Characteristics and Radiological Activities - All Centres

	n	Total (N=XX)
Type of Centre	n	xx
Private		xx (xx.x%)
Public		xx (xx.x%)
Other		xx (xx.x%)
Missing (if applicable)		xx

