*As multiple reasons are possible, the sum of percentage could be greater than 100.

Source: Listing 16.2.6.1.

Table 14.3.1.1 DOTAREM® Administration at Inclusion Visit - Safety Population

		Total (N=XXX)
Total Volume Injected (mL)	n	xxx
	Mean (SD)	xx.xx (xx.xx)
	Median	xx.x
	Min ; Max	xx.x ; xx.x
	Missing (if applicable)	xx
Total Dose Injected (mL/kg)	n	xxx
	Mean (SD)	xx.xx (xx.xx)
	Median	xx.x
	Min ; Max	xx.x ; xx.x
	Missing (if applicable)	xx
Type of Injection	n	xxx
	Manual	xxx (xx.x%)
	Automatic	xxx (xx.x%)
	Missing (if applicable)	xx
Number of Injections	n	xxx
	1	xxx (xx.x%)
	2	xxx (xx.x%)
	Missing (if applicable)	xx
Nature of Package	n	xxx

CONFIDENTIAL	FORM STATISTICAL ANALYSIS PLAN N° DGD-55-003 VERSION N° 2 DATED: 26 FEBRUARY 2018 (REF I011622)	F015830-01 Page 35 / 49
--------------	--	----------------------------

		Total (N=XXX)
	Vial	xxx (xx.x%)
	Pre-Filed Syringe	xxx (xx.x%)
	Vial and Pre-Filed Syringe	xxx (xx.x%)
	Missing (if applicable)	xx
Volume of Vial (mL)	n	xxx
	5 mL	xxx (xx.x%)
	10 mL	xxx (xx.x%)
	15 mL	xxx (xx.x%)
	20 mL	xxx (xx.x%)
	60 mL	xxx (xx.x%)
	100 mL	xxx (xx.x%)
	Missing (if applicable)	xx
Volume of Pre-filled Syringe (mL)	n	xxx
	10 mL	xxx (xx.x%)
	15 mL	xxx (xx.x%)
	20 mL	xxx (xx.x%)
	Missing (if applicable)	xx

SD: Standard Deviation.

%: (n row / n non missing) * 100.

Source: Listing 16.2.5.1.

Table 14.3.2.1 Suspected NSF - Safety Population

		Total (N=XXX)
Suspicion of NSF	n	xxx
	Yes	xxx (xx.x%)
	No	xxx (xx.x%)
	Missing (if applicable)	xx
If Yes,		
Skin*	Burning and Itching	xxx (xx.x%)
	Darkened Patches	xxx (xx.x%)
	Painful Skin Swelling	xxx (xx.x%)
Eyes*	Yellow Raised Spots	xxx (xx.x%)
Bones, Joints and Muscles*	Joint Stiffness	xxx (xx.x%)
	Limited Range of Motion	xxx (xx.x%)

CONFIDENTIAL	FORM STATISTICAL ANALYSIS PLAN N° DGD-55-003 VERSION N° 2 DATED: 26 FEBRUARY 2018 (REF I011622)	F015830-01 Page 36 / 49
--------------	---	----------------------------

		Total (N=XXX)
	Deep Pain	xxx (xx.x%)
	Muscle Weakness	xxx (xx.x%)
	Calcification of the Soft Tissue	xxx (xx.x%)
Systemic Fibrosis*	Fibrosis	xxx (xx.x%)

NSF: Nephrogenic Systemic Fibrosis.

%: (n row / n non missing) * 100, except for multiple answers %: (n row / n with suspicion of NSF) * 100.

*As the suspicion of NSF can be based on multiple topics, the sum of percentage could be greater than 100.

Source: Listing 16.2.9.1.

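### The primary NSF percentage gives a patient lost after one early No the same weight as one assessed at two years, so it cannot alone support a two-year incidence statement

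*SAP*

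**What the plan says.** SAP 1.1 makes NSF incidence the primary objective and gives the time frame: "Patients will be followed during a two-year period after administration of DOTAREM®, to assess if signs or symptoms suggestive of NSF have appeared". Protocol 3.3 sets three reported follow-ups, at 3-12, 13-21 and 22-27 months.

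The planned primary result, in SAP 5.6.2, is: "The number and percentage of patients with any suspicion of NSF will be presented". SAP 5.6 fixes the population: "All safety analyses will be conducted using the SP". SAP 5.2 defines that population with no minimum follow-up: "The safety population (SP) will include all patients receiving at least one injection of contrast media regardless of the quantity". Missed follow-up visits are listed as deviations in SAP 5.2, but no deviation removes a patient from analysis.

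The shell for Table 14.3.2.1 (SAP 7.2) has a single Total column with Yes, No and Missing rows. Its footnote gives the percentage as "n row / n non missing) * 100, except for multiple answers %: (n row / n with suspicion of NSF) * 100". Confirmed NSF appears only in Table 14.3.2.2, as a percentage of biopsied patients. Neither SAP 5.6.2 nor these shells plan a confidence interval, although Protocol 5.2 calls for 95% intervals and SAP 3.3 justifies the sample size by them.

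On dropouts, SAP 3.5 says only this: "No replacement of missing data is planned in this study". Table 14.1.1.1 reports "Number of Patients Prematurely Withdrawn" with reasons, and Table 14.1.1.2 gives attendance by visit. Both use the all-included population, and neither is linked to NSF status.

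**The concern.** A two-year risk needs either two years of observation or a method that accounts for shorter observation. The planned percentage has neither. It uses no person-time, censoring or visit split, and the SAP never says how up to three visit answers become one Yes, No or Missing value. Read plainly, a single No from Follow-up 1 is a recorded No and enters the denominator in full. A patient with no answer at all is Missing and drops out of it.

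The study is meant to confirm a low risk. Time at risk that nobody observed would then be reported as time without suspected NSF. The reader could not tell how much of the denominator this affects. Creatinine, medical events and MRI examinations are tabulated by follow-up visit, but NSF suspicion is not, and Listing 16.2.9.1 has no visit or visit-date column.

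**Working it through.** **1. The plan's own figures.** For 0 cases in n patients the exact two-sided 95% upper limit is 1 - 0.025^(1/n). At n = 1,000 this is 0.368%, which matches the 0.37% in SAP 3.3. The other seven rows of that table also reproduce to the printed decimals (for example 30/1,000: 2.03% to 4.26%).

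**2. The protocol's planning for loss.** Protocol 5.6 accepts a 10% loss (100 of 1,000) and gives a minimum observable frequency of 0.111%. That is 1/(1,000 - 100) = 1/900, so lost patients leave the denominator. With 0 cases in 900 the upper limit is 0.41%. Under the SAP shell, those of the 100 who had given one No would stay in the denominator. SAP 4 does not list this as a change.

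**3. Size of the understatement.** Attrition is not reported, so the inputs are assumptions: a share w of patients with a recorded answer leaves after a Follow-up 1 No at month t, the hazard of suspected NSF is constant and low over 24 months, and leaving is unrelated to risk. Leavers then contribute f = t/24 of the time at risk:

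- crude / true two-year risk = 1 - w(1 - f)
- effective number followed for two years = 1,000 x [1 - w(1 - f)]

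Follow-up 1 runs from month 3 (f = 0.125) to month 12 (f = 0.5). For w = 10% and t = 3: 1 - 0.10 x 0.875 = 0.9125, an effective 912 patients, and a zero-case upper limit of 0.404%.

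| w | Crude / true (t = 3 to t = 12) | Effective n | Upper limit, 0 cases | 5 cases, shown as 0.50%, become |
|---|---|---|---|---|
| 10% | 91% to 95% | 912 to 950 | 0.40% to 0.39% | 0.55% to 0.53% |
| 20% | 83% to 90% | 825 to 900 | 0.45% to 0.41% | 0.61% to 0.56% |
| 30% | 74% to 85% | 738 to 850 | 0.50% to 0.43% | 0.68% to 0.59% |
| 40% | 65% to 80% | 650 to 800 | 0.57% to 0.46% | 0.77% to 0.63% |

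The upper limits apply the exact formula to the effective n, which is an approximation. The nominal 1,000 is itself too favourable: SAP 3.3 and SAP 4 say it was not reached and do not give the number enrolled.

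**4. Exits spread over two years.** Let λ = -ln(0.99)/2 (a true two-year risk of 1%) and μ = -ln(1 - d)/2, with d the share who would leave within two years. The crude percentage is λ/(λ + μ) x [1 - exp(-2(λ + μ))]. It gives 0.95%, 0.90%, 0.84% and 0.78% for d = 10%, 20%, 30% and 40%. If the exits are losses or withdrawals, the gap from 1% is understatement. If they are deaths with patients observed up to death, the same figure is the correct cumulative incidence with death as a competing event.

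**The case against.** The strongest counter-arguments, and what remains of each:

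- **Death.** A reader might infer that every patient who dies after a No pulls the incidence down. Step 4 shows otherwise: a patient observed free of NSF until death is a valid non-case. Only the unobserved interval between the last assessment and death can hide a case. This objection stands.
- **Direction for NSF itself.** A reader might infer that NSF incidence is biased low overall. The percentage is of suspicion, and unconfirmed suspicions push it above NSF incidence. Confirmed NSF is given only per biopsied patient. The understatement concerns ascertainment of suspicion, and the net direction for confirmed NSF is not fixed. This also stands.
- **The reading of the shell.** SAP 5.6.2 states no denominator. The equal weighting is inferred from the footnote to Table 14.3.2.1 and the matching general rule in SAP 3.1. That is fair, but no other rule is given, and the silence itself needs repair.
- **Safeguards.** Protocol 3.3 asks for a check of medical notes when no information could be obtained, at each follow-up. SAP 5.1 treats certain withdrawn patients as not having undergone Follow-up 3, and the disposition tables show withdrawals and attendance. These reduce or reveal the problem but do not change the NSF percentage. SAP 5.1 does not say whether a No from a reclassified patient still counts.
- **Differential loss.** No document shows that leavers are at higher NSF risk, or when within two years the risk falls. A reader might suspect it from withdrawal reasons such as medical decision, but it is not established.
- **Protocol 5.6.** That section is sample size planning and sets no analysis rule. The contrast with the SAP still shows that the planned precision assumed lost patients would not be counted.

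**Conclusion.** The point holds in limited form. The crude percentage ignores length of follow-up and, on the plain reading of the shell, counts patients lost or withdrawn after an early No as non-cases. It therefore understates two-year ascertainment of suspected NSF whenever the hazard after the last assessment is above zero.

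The size depends on attrition that the documents do not report. At the 10% loss that Protocol 5.6 calls acceptable, the effect is small. At 40% it is material: the crude figure would be 65-80% of the true two-year risk. Both rest on a constant hazard, leaving unrelated to risk, and a last assessment at months 3 to 12. With zero cases the estimate is 0% either way, and only the upper limit moves. SAP 5.6.2 does not currently plan that limit.

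The documents do not support saying that the loss was large. They do support saying that no planned NSF output would show whether it was. The repair is a cheap improvement to the primary result.

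**What to change.** Keep Table 14.3.2.1 and add the following to SAP 5.6.2:

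1. A rule for combining up to three visit answers into one status, including whether a No from a withdrawn patient reclassified under SAP 5.1 counts.
2. A table of safety-population patients by last NSF assessment (none, Follow-up 1, 2 or 3) and withdrawal reason. For deaths, show the time from last assessment to death.
3. For suspected and for confirmed NSF separately, either a 24-month cumulative incidence or cases per person-year. In the cumulative incidence, censor losses and withdrawals at the last NSF assessment and treat death as a competing event. Give a 95% confidence interval, exact where possible. With zero cases a variance-based interval has no width, so use an exact limit on person-time.
4. A statement that any two-year incidence claim rests on item 3.

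Do not substitute a denominator of Follow-up 3 completers plus earlier cases unless patients observed free of NSF until death are also kept in it. As an assumed illustration, take 1,000 injected patients, 5 cases and 300 observed NSF-free to death. The cumulative incidence is 5/1,000 = 0.50%, but dropping the 300 gives 5/700 = 0.71%.

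Cost: SAP wording and one extra descriptive table. Visit and withdrawal dates are already in Listings 16.2.1.1 and 16.2.1.2. Listing 16.2.9.1 would need the visit at which each answer was recorded. The stated precision becomes slightly less favourable.

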3. STATISTICAL METHODS

3.1. General considerations

At the end of the study, after the database lock, the statistical analysis will be performed by GUERBET Biostatistic team on the basis of the present document.

A quality control of the statistical analysis will be performed to ensure the reliability of the results.

Thorough description of all parameters reported will be presented. Summary tabulated results will be provided by assessment time if relevant or they will be replaced by the corresponding individual data listings if too few patients are concerned.

Tabulations of quantitative parameters will include the following summary statistics: Number of Patients / Mean / Standard Deviation / Minimum / Median / Maximum. If for a given parameter, the raw value has been collected with x decimal places, the mean, median and standard deviation will be rounded to x+1 decimal places, while the minimum and maximum values will be tabulated as reported with x decimal places.

Tabulations of frequencies for categorical data will include all possible categories and will display the number of observations in a category as well as the percentage (%). Percentages will be rounded to one decimal place. The category missing will be displayed only if there are actually missing values. Percentages will be calculated on the total of recorded (non missing) data.

The **baseline value** will be defined as the last available value prior to administration of the investigational product.

No statistical tests will be performed in this study. All statistics will be only descriptive.

SAS® Version: 9.4 will be used for all descriptive summaries.

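### The SAP's NSF outputs carry no confidence interval and express confirmed NSF only as a percentage of biopsied patients, although the study's aim is to estimate incidence and it was sized on an exact 95% interval

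*SAP*

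**What the plan says.** **Aim.** SAP 1.1 states: "The primary objective of this study is to prospectively estimate the incidence of NSF in patients with moderate to severe renal impairment". Protocol section 2 has the same aim.

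**Sample size.** SAP 3.3 justifies 1000 patients solely by the precision of an exact two-sided 95% interval, tabulated for 0 to 30 cases. Protocol 5.5 has the same intervals and adds a Poisson probability column, but it too argues adequacy from the interval. Protocol 5.2 says that the accuracy of estimates will be shown by two-sided 95% intervals.

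**Denominator.** SAP 5.2 says of the safety population: "This population will be used to evaluate the NSF occurrence". SAP 5.6 adds: "All safety analyses will be conducted using the SP". SAP 3.1 sets the general rule: "Percentages will be calculated on the total of recorded (non missing) data".

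**Planned NSF outputs.** SAP 5.6.2 is a nested chain: suspicion among patients, biopsy among suspected patients, and then "Among patients having a confirmatory biopsy, the number and percentage of patients with a final diagnosis of NSF". The shells follow it. Table 14.3.2.1 gives suspicion over non-missing answers. Table 14.3.2.2 is restricted to suspected patients, and its footnote divides final diagnosis by the number biopsied. No interval appears in SAP 3.1, in 5.6.2, in the table list or in either shell.

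**What was dropped.** SAP 3.1 rules out tests and adds: "All statistics will be only descriptive". SAP section 4 explains that tests are omitted because no comparison can be made, and that the study had lost its power to assess the NSF rate. It does not mention intervals.

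**The concern.** The quantity that the study was designed and sized to deliver is a proportion among patients at risk, with its exact interval. The planned NSF outputs do not contain that pair.

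With a rare outcome, the interval carries most of the information. At zero or very few cases the point estimate says little, whereas the upper limit shows how large an incidence the data leave open. SAP section 4 remarks that the rate of NSF now appears to be under 1%. Whether this cohort can exclude 1% is a question only the interval answers. The one set of intervals in the SAP is the planning table for 1000 patients, a number that was not reached.

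**Working it through.** **Inputs.** Two-sided 95%, exact, one proportion, planned N = 1000 (SAP 3.3; protocol 5.5). The achieved N is below 1000 and not given, so the smaller N below are assumptions.

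**Formula.** Clopper-Pearson, for x cases in n patients:
- lower limit = 2.5% quantile of Beta(x, n − x + 1), or 0 if x = 0
- upper limit = 97.5% quantile of Beta(x + 1, n − x)
- for x = 0 the upper limit reduces to 1 − 0.025^(1/n)

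**Step 1: reproduce the plan's own figures.** For 0/1000, 1 − 0.025^(1/1000) = 0.368%, printed as 0.37%. All eight planning rows reproduce to two decimals, for example 1 case 0.00–0.56%, 10 cases 0.48–1.83% and 30 cases 2.03–4.26%. A one-sided 95% limit at 0/1000 would be 0.30%, so the table is two-sided as stated. The planning arithmetic is sound.

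**Step 2: the same limits at smaller N.** Exact upper 95% limit:

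| n assessed | 0 cases | 1 case | 2 cases |
|---|---|---|---|
| 1000 | 0.37% | 0.56% | 0.72% |
| 900 | 0.41% | 0.62% | 0.80% |
| 500 | 0.74% | 1.11% | 1.44% |
| 400 | 0.92% | 1.38% | 1.79% |
| 300 | 1.22% | 1.84% | 2.39% |

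With zero cases the limit is below 1% only if n exceeds ln(0.025)/ln(0.99) = 367.04, that is, from n = 368.

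**Step 3: what the plan prints if nobody is suspected.** Table 14.3.2.1 shows 0 of n. Because confirmation is nested in suspicion, confirmed NSF is then 0/n as well. The point estimate is available; the upper limit in Step 2 is not.

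**Step 4: what it prints if someone is suspected.** Assume 500 assessed, 2 suspected, and 1 biopsied and confirmed.
- Printed: suspected 2/500 = 0.4%; biopsied 1/2 = 50.0%; final diagnosis 1/1 = 100.0%.
- Not in the NSF outputs: confirmed 1/500 = 0.20% (95% interval 0.01% to 1.11%), and the interval for suspected NSF (0.05% to 1.44%).

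**Step 5: rounding.** SAP 3.1 says: "Percentages will be rounded to one decimal place". At one decimal the zero-case limits at 1000 (0.37%) and at 900 (0.41%) both read 0.4%.

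**The case against.** **The sponsor may have meant to drop intervals.** The protocol's sentence on intervals sits in a section headed as statistical tests. SAP section 4 sets that methodology aside, says that power was lost and that authorities no longer treated NSF as a priority, and SAP 3.1 makes everything descriptive. A deliberate downgrade is therefore possible. But the stated reason is that no comparison can be made, and an interval for one proportion makes none. SAP 3.3 also still repeats the exact-interval rationale. Fewer patients make the interval more necessary. If intervals were meant to go, section 4 should say so.

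**A reader might infer that confirmed NSF can never appear over the safety population, or that the report will hold no incidence estimate.** The documents do not support that. With no suspected patients, 0/N is readable. A confirmed case could also surface in the adverse-event tables, which divide by the safety-population N, because protocol section 4 asks for events behind an SAE report to be entered in the AE section. That route is incidental: SAP 2.3 limits adverse-event collection to routine observation in the MR unit, and those tables carry no interval.

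**A reader might also expect the table to vanish into a listing, or 0.37% to be carried over to a smaller cohort.** Both are speculative. The clause "they will be replaced by the corresponding individual data listings if too few patients are concerned" is general, while Table 14.3.2.2 is specifically listed and shelled. The sentence below the planning table says that 1000 was not reached.

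**Nothing is hidden or lost.** SAP 5.6.2 asks for the number not biopsied and the reasons, and the confirmed count and N remain in the outputs. This stands. However, someone dividing by hand must choose between all treated patients and those with a recorded NSF answer, and the SAP does not settle that for confirmed NSF.

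**Conclusion.** The concern holds in two parts. In every scenario the NSF outputs lack the exact 95% interval on which the study was sized. If at least one patient is suspected, they also lack the confirmed proportion among patients at risk, because the only percentage for confirmed NSF is taken over biopsied patients.

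The omitted zero-case upper limit is 0.41% at 900, 0.74% at 500, 0.92% at 400 and 1.22% at 300, against 0.37% at the planned 1000. These rest on assumed N, since the documents give neither the achieved N nor the numbers suspected, biopsied or confirmed. The conclusion that an interval is missing depends on none of them. This is a gap in planned reporting that SAP wording can close; it is not an error in the planning calculation or a loss of data.

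**What to change.** 1. In SAP 5.6.2 and the NSF tables, add a primary line: patients finally diagnosed with NSF, over safety-population patients with a non-missing answer on NSF suspicion (the SAP's own non-missing rule), with a two-sided Clopper-Pearson 95% interval. Report it also when the count is zero, and print it to two decimals.
2. Beside it, give the safety-population N and the number with an NSF answer at follow-up 3. Under the non-missing rule a patient seen only at follow-up 1, possibly at 3 months, counts in full. These two numbers keep the interval from being read as complete two-year follow-up for everyone.
3. Put the same interval on the suspected-NSF line of Table 14.3.2.1, as a bound that includes suspected patients who were not biopsied.
4. State in SAP section 4 that intervals are kept although tests are dropped, and quote the precision at the number actually assessed.

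The cost is SAP wording, one new line with its two counts, and one further interval, all from data already collected. The downside is slightly more output and a stated precision less favourable than 0.37%.
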